To inform our sample size estimation for this feasibility randomized controlled trial, we used the available literature which reported a 7% treatment success rate at 4-weeks following a single, standard exercise session (ie. non-load modifying)⁶ and the hypothesized 70% treatment success rate following an 8-week to a supervised load modification program.¹⁸ Conservatively, we estimated that the standard exercise (SE) group and load modification (LM) group would have a 20% and 50% success rate, respectively. **With one-side type I error=0.1, power=80%, and allocation ratio is 1:1, we will need 22 participants in each group (total N=44). We will recruit 64 individuals with GTPS to account for up to 30% attrition over the course of the study due to drop-out.** To fully recruit the study after proper regulatory approval is in place and staff are trained, we anticipate a 15-month recruitment time-frame for the 60 participants. This factors in a recruitment rate of 5 participants per month (see Letters of Support/Collaboration), from an eligible 10 (minimum 50% recruitment rate).

Recruitment and Informed Consent (Figure 1): Prior to enrollment, written informed consent will be obtained from all potential participants after information about the purpose, methods, and demands of the study is provided both verbally and in writing (via the consent documentation) to the participant. The participants for this trial will be recruited from the Jameson Crane Sports Medicine Institute physician clinics at OSUWMC during their on-site medical visit. Once the treating physician confirms GTPS diagnosis through our standardized and validated clinical examination process (Table 1, Inclusion Criteria),^{18,31} the study recruiter will then discuss the study opportunity with the patient and proceed with the consenting process when appropriate.

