b. Activity modifications instructions for the load modification group: This instruction will take approximately 5 additional minutes based on our use of this handout in our physical therapy clinic with patients with GTPS for the past 2 years.

i. **Posture and movement handouts:** The physical therapist will share the handout (Appendix 2. Supplements – Lateral Hip Pain Activity Modifications) with the participant, asking them to identify any of the movements or postures (ie. sitting with legs crossed, iliotibial band stretching) that are common to their daily activities. Patients will be educated as to how each contributes to increased pressure on the lateral structures of hip and can cause pain. The physical therapist will review, demonstrate, and provide feedback on all items relevant to the participants' daily routine.

ii. **Using pain as a load modification guide:** Participants in the load modification group will be instructed not to exceed 5 out of 10 on the NPRS during the exercises, and proceed with training as long as this pain intensity during exercise does not increase their pain in within the next 24 hours.¹³

iii. **Changes to activity level:** participants in the load modification group who report >5/10 pain with exercise that does not change or is worse the next day will be advised to reduce their physical exercise activity (ie. walking, hiking, running).¹³ Participants in the load modification group will also be instructed to modify activity level as needed to avoid increasing pain or stiffness each week. Participants randomized to the standard exercise group will be instructed to avoid the painful physical exercise activity for the duration of the 4-week program (ie. "If it hurts, don't continue to do it. Focus on these few exercises for the 4 weeks). Activity level will be monitored using the Tegner Activity Level Scale on a weekly basis over the 4-week intervention.⁴³

F. Weekly online/telephone surveys: Participants will be asked to complete a REDCap™ survey (Appendix 2. Supplements – Weekly Survey) each week until their follow-up visit to the Jameson Crane Sports Medicine Institute for study testing and their clinical visit. This weekly survey will include the GROC, the NPRS, and home exercise program compliance questions. It will also include questions about any treatment they have received or injuries they have had that may affect the outcomes of interest.

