Post collection data storage and analysis: A blinded study team member will be responsible for 2D video quality control and creating trial clips for subsequent analysis. Video analysis will begin after the last participant completes their 4-week follow-up. These data will be used to determine measurement variability (intraclass correlation coefficients, standard error of the measurement, and minimal detectable change values) and provide information with regard to changes in movement patterns as a result of program participation. Frontal plane kinematics (peaks and excursions) of the trunk, pelvis, hip, and knee will be calculated (Kinovea version 0.8.15) for each task. Analysis will include the double and single leg static starting postures and peak frontal plane motion (as identified using the joint position tracking function). Lines will be drawn through the long axes of the bones for the shank and thigh, through the ASIS for the pelvis, and from the sternum to the midpoint of the ASIS line (Figure 2). Horizontal and vertical 'lab axes' will be applied to the image to allow calculations relative to pure horizontal (ie. pelvic drop) and pure vertical (ie. trunk lean). Angles will also be calculated with respect to the proximal segment.

Statistical analysis plan:

An intention to treat approach is planned for all analyses, using all participants who were randomized who have available data at 4 week follow-up. Where appropriate, normality will be assessed and non-parametric approaches will be used when assumptions are violated. Demographics and clinical characteristics (ie. age, sex distribution, BMI, baseline pain scores, etc) will be summarized for SE and LM groups, respectively, and compared between the groups using two-sample t-test for continuous outcomes or Fisher's exact test for discrete outcomes.

To evaluate the effect of treatment group allocation on dichotomized treatment success (Aim 1, Hypothesis 1), defined as either: 1) at least 'moderately better' on the Global Rating of Change scale or 2) ≥ 2 point decrease on the Numeric Pain Rating Scale, we will use Fisher's exact test to compare the success rate between SE and LM group. Frontal plane kinematics are a secondary variable of interest (Aim 1, Hypothesis 2). With the available 2D data set, we will compare change scores between groups using independent t-tests and/or effect sizes. These data may serve as preliminary data for future grant applications.

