To evaluate study retention rates and treatment adherence (Aim 2) we will use descriptive statistics. We will calculate the number of participants in each treatment group who report completing the home program "most (4+) days of the week" and "mostly as directed" on each of the four (4) follow-up REDCap™ surveys. The retention rate and compliance rate will be calculated with 95% confidence interval using exact binomial for each treatment at each follow-up.

H. Feasibility: We will evaluate the feasibility of a future clinical trial to determine the efficacy of load modification exercises and education in improving post-operative function in patients with GTPS by quantifying:

1. The proportion of recruited participants from the total number (a) screened and (b) eligible
2. Participant adherence as measured by: (1) number of weekly surveys completed (ie. number of surveys completed/total number of surveys, (2) weekly home exercise program compliance (self-reported) over the duration of the study, (3) participation retention/attendance at the 4-week follow-up session, and (5) reasons for drop-out and when it occurred (e.g. participant moved out of the area prior to 4-week follow-up)

I. Potential Problems/Alternative Strategies

1. MRI will not be used to confirm gluteal tendinopathy. Grimaldi and colleagues (2017)³¹ performed a diagnostic utility study of 65 individuals with GTPS that showed pain during a 30 second single limb stance was strongly associated with MRI-confirmed gluteal tendinopathy (+LR = 12.2). Importantly, literature also confirms the high prevalence of MRI-confirmed gluteal tendinopathy in asymptomatic individuals,^{31,44,45} highlighting the absence of a strong association between imaging-identified tissue pathology and the clinical syndrome of GTPS. For the aims of this study, this and other validated clinical tests will be used to identify individuals with GTPS. We accept that a small, but insignificant proportion of enrolled participants with clinical indicators of GTPS may not have radiologically-confirmed gluteal tendinopathy. We do not anticipate this will affect the results of this study.

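### The SAP's single analysis set, randomized participants with 4-week data, is applied to all analyses with no exception for Aim 2, so read literally it fixes 4-week retention at 100% and drops later leavers from weekly compliance

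*Combined protocol and SAP*

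**What the plan says.** The Statistical analysis plan opens with one population rule: "An intention to treat approach is planned for all analyses, using all participants who were randomized who have available data at 4 week follow-up".

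The Aim 2 paragraph of the same section counts, per arm, the participants who report adequate home-programme completion "on each of the four (4) follow-up REDCap™ surveys". It then adds: "The retention rate and compliance rate will be calculated with 95% confidence interval using exact binomial for each treatment at each follow-up". It gives no denominator, no rule for a missed survey and no exemption from the opening sentence.

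Other sections bear on this:
- Section F schedules the surveys "each week until their follow-up visit", so a participant who leaves early may already have supplied compliance reports.
- Section H (Feasibility) lists survey completion ("number of surveys completed/total number of surveys") and "participation retention/attendance at the 4-week follow-up session" as measures of their own, together with the reasons for and timing of drop-out.
- Benchmarks for success sets 80% retention at 4 weeks.
- Section A (Sample size estimation) allows for up to 30% attrition.

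**The concern.** A retention rate has to be taken over people who could have been lost. The stated set keeps only people who were not lost. Applied to Aim 2 as written, it makes the 4-week retention figure uninformative and the 80% benchmark impossible to fail.

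The same rule removes valid week 1 to 3 compliance reports from anyone without 4-week data. People who give up the programme may well be the ones who stop responding, so the remaining rate would tend to look better than adherence in everyone assigned. The distortion would differ between arms if drop-out did.

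Retention and adherence are the stated content of Aim 2 in a feasibility trial, and these are figures that planners of the later trial would carry forward. An exact binomial interval also cannot be pre-specified without its n.

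**Working it through.** **1. The plan's own figures.** The documents state no expected compliance rate, so no Aim 2 figure can be reproduced. The sample size can, and it supplies the arm size used below. Section A assumes that the standard exercise and load modification groups "would have a 20% and 50% success rate, respectively", and states: "With one-side type I error=0.1, power=80%, and allocation ratio is 1:1, we will need 22 participants in each group (total N=44".

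Using the normal approximation with pooled variance under the null:

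n = [1.2816 × √(2 × 0.35 × 0.65) + 0.8416 × √(0.20 × 0.80 + 0.50 × 0.50)]² / 0.30² = (0.8645 + 0.5389)² / 0.09 = 21.9, so 22 per arm (power 0.802).

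For 30% attrition, 22 / 0.70 = 31.4, so 32 per arm, or 64 in total. The stated figures reproduce.

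**2. Retention under the literal set.** The numerator and denominator are the same people.

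| Retained of 32 | Over all randomized (exact 95% CI) | Over the stated set (exact 95% CI) |
|---|---|---|
| 22 (near 30% attrition) | 68.8% (50.0-83.9) | 22/22 = 100% (84.6-100) |
| 26 (near the 80% benchmark) | 81.3% (63.6-92.8) | 26/26 = 100% (86.8-100) |

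This takes retention to mean having 4-week data. If it means attendance, a few participants might give 4-week data remotely without attending. The rate could then fall slightly below 100%, but those lost altogether would still be excluded.

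**3. Compliance.** Assumptions: 32 randomized per arm, and about 80% compliance among completers. Let m be the number retained, x the compliant completers, and N = 32.

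- Completer rate = x/m.
- All-randomized rate if no leaver complied = x/N, which equals the completer rate times retention.
- All-randomized rate if every leaver complied = (x + N − m)/N.

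| m | x/m (exact 95% CI) | No leaver compliant (exact 95% CI) | All leavers compliant |
|---|---|---|---|
| 22 | 18/22 = 81.8% (59.7-94.8) | 18/32 = 56.2% (37.7-73.6) | 28/32 = 87.5% |
| 26 | 21/26 = 80.8% (60.6-93.4) | 21/32 = 65.6% (46.8-81.4) | 27/32 = 84.4% |

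**4. Sensitivity to the assumed rate.** For completer compliance of roughly 60% to 90%, the gap to the no-leaver-compliant bound is 18.5 to 28.4 points with 22 retained, and 11.5 to 16.6 points with 26 retained.

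**5. Direction.** The completer rate is too high only if leavers comply less often than completers. With 18/22 compliant, it overstates when at most 8 of the 10 leavers comply, since (18 + 8)/32 = 81.3% is below 81.8%. At 9 or 10 it understates. If 4 of the 10 comply, the rate is 22/32 = 68.8%, a gap of 13 points rather than 26.

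**6. Arm size of 30.** Some passages of the protocol use 60 participants in total. With 21 of 30 retained and 17 compliant, the completer rate is 17/21 = 81.0%, against 17/30 = 56.7% to (17 + 9)/30 = 86.7%. The conclusion does not depend on 32 or 30.

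**The case against.** The strongest reply is that the sponsor cannot have meant the 4-week-data set for Aim 2. The plan reports a retention interval, sets a retention benchmark and records drop-out, none of which makes sense in a set of completers. Compliance stands in the same sentence as retention, and reporting at each follow-up fits a denominator of all randomized, or of that week's responders, at least as well. The kinematic analysis, too, is tied to whatever 2D data are available.

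Much of this stands as a statement of intent. It does not rescue the text: it concedes that the one population rule given for all analyses fails for half of that sentence, and it leaves compliance with three candidate denominators and no choice among them.

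A reader might infer something stronger: that the reported compliance rate definitely is a completers' rate, and that it overstates adherence by some 26 points. The documents do not support that. The completer denominator is a literal reading, not a declared choice for compliance. Nothing in the plan says that leavers comply less; its own example of drop-out is a participant moving away. The 82% against 56% contrast requires that none of the ten leavers complied, which is least plausible in weeks 1 to 3, when they may still have been answering.

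Two further objections stand. Survey completion, attendance and drop-out are reported separately, so a reader could see the loss, although this alters neither the compliance rate nor its interval. And none of the three success benchmarks uses compliance, so no benchmark turns on that rate.

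**Conclusion.** The point holds as a defect in the stated rule. Followed as written, the SAP makes 4-week retention 100% by construction, leaves the 80% benchmark untestable, and discards weekly compliance reports from participants who later leave. Upward bias in compliance is likely but unproven.

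The size rests on assumed counts. A completer rate near 82% is compatible with an all-randomized rate anywhere from 56% to 88% when 22 of 32 are retained. A rate near 81% is compatible with 66% to 84% when 26 of 32 are retained. The lower ends are bounds, not estimates. Aim 2 is descriptive, and the Aim 1 test is unaffected.

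**What to change.** Amend the Statistical analysis plan as follows:

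- Limit the set with 4-week data to the Aim 1 outcome comparisons.
- State that Aim 2 retention is taken over all participants randomized to the arm.
- State that weekly compliance uses every survey received, including those from participants who later leave.
- Report weekly compliance in two ways, each with its exact binomial interval: over all randomized, with a missing survey counted as not compliant and the result labelled a conservative bound; and among that week's responders.

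The cost is wording only, with no added visits or data. The downside is a less favourable adherence figure. The all-randomized rate also mixes survey response with adherence, because it scores someone who exercised but skipped the survey as non-compliant. That is why both rates should be shown.
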